1. INTRODUCTION

1.1 BACKGROUND

Aramchol is a novel conjugate of cholic acid (bile acid) and arachidic acid (saturated fatty acid), linked by a stable amide group. It is in development for treatment of nonalcoholic steatohepatitis (NASH) and fibrosis. Aramchol affects stearoyl coenzyme A desaturase 1, a key liver enzyme involved in regulating lipid metabolism. In animal models of NASH, it reduces steatosis, ballooning, inflammation, and fibrosis by down-regulation of stearoyl coenzyme A desaturase 1 expression in hepatocytes and hepatic stellate cells.

Aramchol is highly lipophilic and pharmacokinetic (PK) studies in humans show that plasma concentrations increase less than proportionally to dose due to poor absorption. Its mean terminal phase half-life ($t_{1/2}$) is approximately 3 days but most of the drug is cleared with a $t_{1/2}$ of about 35 hours and steady state on repeat dosing is achieved within 7 to 10 days. Aramchol is secreted in bile and is excreted in feces. [REDACTED]

[REDACTED]

[REDACTED]

[REDACTED] Two

Phase 2 clinical studies have been completed including a placebo-controlled study in which subjects with NASH were treated for 52-weeks. Significantly more subjects who received aramchol 600 mg daily showed NASH resolution without worsening of fibrosis and a larger proportion of subjects showed at least a 1-point improvement in fibrosis score without worsening of steatohepatitis.

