3. STUDY DESIGN

This is a Phase 1, multicenter, open-label, 2-part, single- and multiple-dose study designed to assess the effect of hepatic insufficiency on the PK of aramchol.

Each part of the study will consist of a screening period, a check-in day, a treatment period, and an end-of-study (EOS) visit.

In Part 1 (single-dose), up to 48 subjects are planned: 8 subjects each in the mild (Cohort A), moderate (Cohort B), and severe (Cohort C) hepatic impairment cohorts and 8 to 24 healthy control subjects with normal hepatic function (Cohort D). Enrollment of 8 subjects with mild hepatic impairment (Cohort A) will proceed only if there is evidence of reduced clearance of aramchol in Cohort B. At screening, subjects will be assigned to a study cohort according to the Child-Pugh classification system as follows:

Cohort	Hepatic Condition	Child-Pugh Grade	Number of Subjects
A ^(a)	Mild impairment	Class A (Score of 5 to 6)	8
B	Moderate impairment	Class B (Score of 7 to 9)	8
C	Severe impairment	Class C (Score of 10 to 15)	8
D	Healthy (control)	—	8 to 24

^(a) Enrollment of subjects into Cohort A will only proceed if there is evidence of reduced clearance of aramchol in Cohort B.

Healthy control subjects (Cohort D) will be matched with hepatically impaired subjects (Cohorts A, B, and C) according to gender, age (± 10 years), and body mass index (BMI) ($\pm 20\%$).

Safety data and PK profiles of aramchol from at least 4 subjects with moderate hepatic impairment (Cohort B) will be obtained and reviewed while enrollment to this cohort continues. These 4 subjects in Cohort B must demonstrate satisfactory safety (no serious AEs [SAEs] or severe AEs related to aramchol) and PK results for up to 4 days after dosing before enrollment of subjects with severe hepatic impairment (Cohort C) is initiated. Two subjects with severe hepatic impairment must demonstrate satisfactory safety and tolerability (no SAEs or severe AEs related to aramchol) for up to 4 days after dosing before the remaining subjects with severe hepatic impairment may be dosed.

Enrollment of subjects to Cohort A (mild hepatic impairment) will proceed only if there is evidence of reduced clearance of aramchol in the first 4 subjects in Cohort B (moderate hepatic impairment), defined as a reduction in apparent total oral clearance (CL/F) of greater than 30% compared with values in historical healthy control subjects.

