In Part 2, a cohort of at least 8 subjects comprising of mild and moderate or moderate and severe hepatic impairment subjects will be administered aramchol as multiple doses to obtain the PK profile of aramchol at steady state. A decision on the severity of hepatic impairment of subjects to participate in Part 2 (multiple-dose) will be made by the sponsor based on the available safety and PK results from Part 1 (single-dose).

Healthy control subjects will be matched with the hepatically impaired subjects according to gender, age (± 10 years), and BMI ($\pm 20\%$).

Single Dose (Part 1):

On Day 1, subjects will receive a single oral dose of 600 mg aramchol administered with 240 mL of water in the morning, after an overnight fast of at least 10 hours, and approximately 30 minutes after consuming a standardized breakfast. Subjects will remain fasted except for water for 2 hours after dosing. During the study, subjects may consume water on an ad libitum basis. Hepatically impaired subjects will receive a diet standardized for hepatic impairment and healthy control subjects will receive a similar diet.

Serial blood samples for PK analysis of aramchol concentrations in plasma will be collected before dosing (0 hour) and up to 168 hours for healthy subjects and 240 hours for hepatically impaired subjects after administration of aramchol.

Subjects will be confined to the clinical site from Day -1 until discharge on Day 8 for healthy control subjects and on Day 11 for hepatically impaired subjects. The duration of the study, excluding screening, is approximately 23 days.

Multiple Dose (Part 2):

Multiple dosing will involve twice daily (approximately 12 hours apart) oral administration of aramchol for 11 days with a single AM dose on Day 12 to achieve steady state. The dosage will not exceed 300 mg twice daily but may be adjusted to give lower exposure depending on review of available data on any reduction in clearance associated with hepatic impairment seen with single doses in Part 1. Subjects will consume a standardized meal 30 minutes prior to the AM and PM doses of aramchol. Subjects will remain fasted except for water for 2 hours after dosing. During the study, subjects may consume water on an ad libitum basis. Hepatically impaired subjects will receive a diet standardized for hepatic impairment and healthy control subjects will receive a similar diet.

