6.1 PHARMACOKINETIC ASSESSMENTS AND ENDPOINTS

Single Dose (Part 1):

Blood samples for analysis of concentrations of aramchol and its metabolites in plasma will be collected at the following time points: before dosing (0 hour) and at 1, 2, 3, 4, 5, 6, 8, 10, 12, 14, 18, 24, 48, 72, 96, 120, 144, 168, 192, and 240 hours (the last 2 time points are for hepatically impaired subjects only) after administration of aramchol. Acceptable time deviations are ± 5 minutes for 0 to 4 hours, ± 10 minutes for >4 to 8 hours, ± 15 minutes for >8 to 24 hours, ± 30 minutes for >24 to 72 hours, and ± 60 minutes for >72 hours to 240 hours.

The following plasma PK parameters will be calculated as endpoints for aramchol using actual sampling times rather than scheduled sampling times:

- AUC from time 0 to the last quantifiable concentration (AUC_{0-t})

- AUC from time 0 extrapolated to infinity (AUC_{0-inf})
- Maximum observed plasma concentration (C_{max})
- Time to reach maximum observed plasma concentration (T_{max})
- Time to the first measurable plasma concentration (T_{lag})
- Apparent terminal elimination half-life ($t_{1/2}$)
- Apparent oral clearance (CL/F)
- Apparent volume of distribution (V_z/F)
- Elimination rate constant (k_e)

Multiple Dose (Part 2):

Blood samples for analysis of concentrations of aramchol and its metabolites in plasma will be collected before the AM dose on Days 1, 4, 8, 9, 10, 11, and 12 and at the following times after the AM dose on Day 12: 1, 2, 3, 4, 5, 6, 8, 10, and 12 hours. Acceptable time deviations are ± 5 minutes for 0 to 4 hours, ± 10 minutes for >4 to 8 hours, and ± 15 minutes for >8 to 12 hours.

The following plasma PK parameters on Day 12 will be calculated as endpoints for aramchol using actual sampling times rather than scheduled sampling times (if conducted):

- AUC from time 0 to the dosing interval tau at steady state ($AUC_{0-tau, ss}$)
- Maximum observed plasma concentration at steady state ($C_{max, ss}$)
- Time to reach maximum observed plasma concentration at steady state ($T_{max, ss}$)
- Minimum observed plasma concentration at steady state ($C_{min, ss}$)
- Time of minimum observed plasma concentration at steady state ($T_{min, ss}$)
- Average plasma concentration at steady state ($C_{avg, ss}$)

Time to reach steady state will also be estimated graphically by assessing trough plasma concentrations (ie, pre-AM dosing on Days 1, 4, 8, 9, 10, 11, and 12) over 12 days of administration.

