7.3.1 Pharmacokinetic Analyses

Plasma concentrations will be listed and summarized descriptively (number of subjects, arithmetic mean, SD, coefficient of variation [CV], minimum, median, and maximum). Plasma concentration versus actual time profiles for each subject will be presented graphically. The mean plasma concentration versus scheduled time profiles will be presented graphically.

Pharmacokinetic parameters derived from plasma concentration data using noncompartmental methods with Phoenix[®] WinNonlin[®] (Certara USA Inc, Princeton, New Jersey) Version 8.0 or higher will be summarized by hepatic group using descriptive statistics (number of subjects, arithmetic mean, SD, CV, minimum, median, and maximum). Geometric mean and geometric CV will also be calculated for AUCs and C_{max} . The AUC_{0-t} , AUC_{0-inf} , and C_{max} values may also be expressed in terms of unbound drug concentrations.

An analysis of variance (ANOVA) model will be performed on the natural logarithms of AUC_{0-t} , AUC_{0-inf} , and C_{max} to calculate the ratio of geometric means and its 90% confidence interval between subjects with hepatic impairment and the corresponding healthy control

subjects, as appropriate. The ANOVA model will include hepatic group (normal matching mild, mild, normal matching moderate, moderate, normal matching severe, and severe, where applicable) as a fixed effect.

For AUC_{0-t} , AUC_{0-inf} , and C_{max} , a linear regression model will be performed on the natural logarithms of AUC_{0-t} , AUC_{0-inf} , and C_{max} as dependent variables and each of the following natural-log-transformed hepatic function estimates as independent variables: Child-Pugh classification score (in subjects with hepatic impairment only), baseline serum bilirubin, serum albumin, and prothrombin time. The regression coefficients representing the relationship between the PK parameters and the hepatic function estimates will be estimated together with their 90% confidence intervals from the regression model.

Sensitivity analyses may be conducted to investigate the potential impact of imbalance existing across hepatic impairment groups in the distribution of the baseline covariates used in subject matching (eg, body weight) and, if data suggest, appreciable differences in PK exposure (AUC_{0-t} , AUC_{0-inf} , and C_{max}) across different values of the same baseline covariate.

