Detailed descriptions of the analyses in this study will be presented in the statistical analysis plan.

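### In Part 1, AUC0-t can run to 240 h in impaired subjects but stops by 168 h in healthy controls, so its ratio can exceed 1 with identical kinetics

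*Combined protocol and SAP*

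**What the plan says.** Section 3 (Single Dose, Part 1) sets plasma sampling "up to 168 hours for healthy subjects and 240 hours for hepatically impaired subjects". Section 6.1 lists the times and states that "the last 2 time points are for hepatically impaired subjects only"; these are the 192 h and 240 h samples. The schedule of events in Section 3.1 agrees.

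Section 6.1 defines AUC0-t as "AUC from time 0 to the last quantifiable concentration". No fixed cut-off time is attached.

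Section 7.3.1 states: "An analysis of variance (ANOVA) model will be performed on the natural logarithms of" AUC0-t, AUC0-inf and Cmax. The output is the impaired/healthy ratio of geometric means with a 90% confidence interval. The same three log parameters are regressed on "Child-Pugh classification score (in subjects with hepatic impairment only), baseline serum bilirubin, serum albumin, and prothrombin time". Only the Child-Pugh regression is limited to impaired subjects.

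The rules for BLQ and missing values in Section 7.4 do not align the sampling windows. No section defines a common-window AUC or ranks the exposure measures. Section 7.3.1 ends by deferring detail: "Detailed descriptions of the analyses in this study will be presented in the statistical analysis plan". That separate plan is not among the documents.

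**The concern.** AUC0-t is a like-for-like quantity only when both groups are followed for the same time, or when drug is unquantifiable in everyone before the shorter follow-up ends. Neither is assured here. Any area between 168 h and 240 h is positive, and only impaired subjects can contribute it. With no effect of hepatic impairment, the error therefore always pushes the ratio up.

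Two analyses are exposed. The ANOVA ratio for AUC0-t mixes exposure with length of sampling. Any regression of ln(AUC0-t) on bilirubin, albumin or prothrombin time that pools healthy and impaired subjects has the same problem, because length of sampling follows group and so tends to follow the liver tests.

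The practical risk is a misread AUC0-t ratio when the true effect is small, or AUC0-t and AUC0-inf ratios that disagree with no rule for which one to believe.

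**Working it through.** The plan states no expected AUC0-t ratio, so there is no figure to reproduce.

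**Inputs**
- Last sample: 168 h healthy, 240 h impaired (Sections 3 and 6.1).
- Half-lives (Section 1.1): the terminal value is "approximately 3 days but most of the drug is cleared with a" half-life of about 35 h. I use 72 h and 35 h.
- 8 subjects per impaired cohort (Section 7.1).
- Not given, so assumed: the share of area in the 72 h phase (0 to 1), the assay limit, and the between-subject CV (30% to 60%).

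**Step 1: ratio when both groups have identical kinetics.** For one phase with half-life h, the fraction of total AUC captured by time T is 1 − 2^(−T/h).

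| Half-life | by 168 h | by 192 h | by 240 h | 192/168 | 240/168 |
|---|---|---|---|---|---|
| 35 h | 0.964 | 0.978 | 0.991 | 1.014 | 1.028 |
| 72 h | 0.802 | 0.843 | 0.901 | 1.051 | 1.124 |

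For a mixture with share f of the area in the 72 h phase, captured(T) = (1 − f)(1 − 2^(−T/35)) + f(1 − 2^(−T/72)). The ratio captured(240)/captured(168) is 1.036 (f = 10%), 1.049 (25%), 1.072 (50%) and 1.091 (70%). Section 1.1 says most of the drug clears with the 35 h half-life. Reading that as f below 50% gives 1.03 to 1.07.

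**Step 2: check on the protocol's sampling times.** A noncompartmental calculation (assumed absorption rate 0.5/h, linear-up log-down, last four points for the terminal slope) gives:
- AUC0-t ratio 1.030 (35 h) to 1.127 (72 h);
- AUC0-inf ratio 1.000 to 1.012;
- area extrapolated 3.7% to 20.2% in healthy subjects and 0.9% to 10.1% in impaired subjects;
- concentration at 192 h of 2.7% (35 h) to 17.4% (72 h) of Cmax. If the assay limit lies above that level, AUC0-t ends by 168 h in both groups and the artefact disappears.

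**Step 3: size against precision.** With 8 v 8, the 90% interval factor is exp(t(0.95, 14 df) × σ × √(2/8)), where σ = √ln(1 + CV²) and t = 1.761.
- CV 30%: σ = 0.294, factor 1.30.
- CV 60%: σ = 0.555, factor 1.63.

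The chance that the lower 90% limit exceeds 1 with no true effect is nominally 5%. It becomes 6% to 7% at a shift of 1.03, 7% to 8% at 1.04, and 9% to 14% at 1.09. The protocol defines no such test; this only gauges how often a reader would see an interval above 1.

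**Step 4: behaviour under a real effect.** Assume one phase, with half-life lengthening as 1/CL. The AUC0-t ratio is (1/CL) × [1 − 2^(−240·CL/h)] / [1 − 2^(−168/h)], where CL is clearance relative to healthy subjects. For AUC0-168, replace 240 by 168.

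| Fall in CL/F | True ratio | AUC0-t, 35 h / 72 h | AUC0-168, 35 h / 72 h |
|---|---|---|---|
| 0% | 1.00 | 1.03 / 1.12 | 1.00 / 1.00 |
| 30% | 1.43 | 1.43 / 1.43 | 1.34 / 1.21 |
| 50% | 2.00 | 1.88 / 1.71 | 1.68 / 1.38 |

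AUC0-t is exact at a 30% fall because 168/240 = 0.70. AUC0-168 is the closer of the two only for falls below about 13% (35 h) to 15% (72 h).

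**The case against.** The strongest reply is that the longer window suits the effects this study looks for. The one quantitative PK threshold in the protocol is the condition for opening Cohort A, "defined as a reduction in apparent total oral clearance (CL/F) of greater than 30% compared with values in historical healthy control subjects", and at a 30% fall the planned AUC0-t reads correctly. For larger falls it understates less than AUC0-168 does. This stands. It is a reason to keep the 240 h samples and not to replace AUC0-t with AUC0-168. It does not justify an uncaveated ratio, because AUC0-t is accurate only near that one effect size: too high below it, too low above it.

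No stated decision uses AUC0-t, and AUC0-inf is already in the same models. Both points are true and limit the harm. However, three exposure measures stand side by side with no lead, and Section 3 leaves the choice of severity groups for Part 2 to the available safety and PK results without naming a measure.

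The shift is small beside the confidence interval, and the figures of 1.09 and 1.12 need more area in the 72 h phase than Section 1.1 suggests. That also stands; 1.03 to 1.07 is the better range. The error is nonetheless systematic, so more subjects would narrow the interval without removing it.

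Finally, the assay limit is unknown and a separate SAP may deal with the matter. Both are conditions on the conclusion.

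**Conclusion.** The concern holds. As written, if aramchol is quantifiable at 192 h or later, the impaired/healthy AUC0-t ratio is above 1 when hepatic impairment has no effect. With drug quantifiable to 240 h, the excess is 3% to 7% if most of the area lies in the 35 h phase, and at most about 12% to 13% if all of it lies in the 72 h phase. If the last quantifiable sample is at 192 h, the excess is 1% to 5%. If concentrations are below the assay limit by 192 h, there is none.

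The direction under no effect is certain given quantifiable late drug; the size rests on the Section 1.1 half-lives and an assumed split between phases. Cmax is unaffected, AUC0-inf shifts by 1.2% at most in the model used, and the Cohort A rule uses CL/F. This should be fixed because it touches the primary comparison and costs little, but it does not threaten the study's main conclusions.

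**What to change.** In Section 7.3.1, or in the separate SAP if it does not already cover this:

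1. Name AUC0-inf as the main exposure measure for the ANOVA and the regressions, and report the percentage extrapolated by group.
2. Report AUC0-t descriptively, or keep its ratio with a stated caveat that sampling ends at 168 h in healthy subjects and 240 h in impaired subjects.
3. Add AUC0-168 in both groups as a supportive like-for-like comparison, not as the main measure.
4. State its limitation: it reads 1.00 under no effect but understates real effects when elimination slows, as the 30% and 50% rows above show.

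The cost is a few sentences and one partial AUC from samples already planned; no extra blood draws, visits or subjects are needed. The trade-off is that AUC0-inf depends on extrapolation, about 4% to 20% of the area in healthy controls against 1% to 10% in impaired subjects under identical kinetics. That is why the percentage should be shown. The choice should be fixed before the PK data are reviewed, since the study is open-label.

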3.1 SCHEDULE OF EVENTS - SINGLE DOSE ARAMCHOL (PART 1)

Procedure ^(a)	Phase Day	Screening	Check-in	Treatment Period										EOS	
		-28 to -2	-1	1	2	3	4	5	6	7	8	9	11	22 (±2)	
Admission to clinic			X												
Discharge from clinic											X ^(b)		X ^(c)		
Outpatient visit ^(d)														X	
Informed consent		X													
Demographics		X													
Serology ^(e)		X													
Serum FSH ^(f)		X													
Inclusion/exclusion criteria		X	X												
Medical history		X	X												
Height, weight, and BMI ^(g)		X	X											X	
Physical examination ^(h)		X	X											X	
Vital sign measurements ⁽ⁱ⁾		X	X	X	X	X	X				X ^(j)		X ^(k)	X	
12-lead ECG ^(l)		X	X	X	X		X				X ^(j)		X ^(k)	X	
Clinical laboratory testing ^(m)		X	X				X				X ^(j)		X ^(k)	X	
Urine drug/alcohol screen ⁽ⁿ⁾		X	X												
Urine pregnancy test ^(o)		X	X											X	
Aramchol administration ^(p)				X											
PK blood sample collection ^(q)				X	X	X	X	X	X	X	X	X ^(k)	X ^(k)		
Adverse events ^(t)		← X →													
Prior/concomitant medications		← X →													

Abbreviations: AE, adverse event; BMI, body mass index; ECG, electrocardiogram; EOS, end of study; FSH, follicle-stimulating hormone; PK, pharmacokinetic.

Notes:

- (a) When procedures overlap or occur at the same time point, all blood draws should follow vital sign measurements or ECGs, and PK sampling should be timed to occur last and as close to the scheduled time window as possible.
- (b) Discharge following all study procedures on Day 8 for healthy control subjects.
- (c) Discharge following all study procedures on Day 11 for hepatically impaired subjects.
- (d) An EOS visit will occur 11 days after the Day 11 (240-hour) PK blood sample.
- (e) A complete list of serology assessments is provided in Section 6.2.2.
- (f) Females only. Further details are provided in Section 6.2.2.
- (g) Height and weight will be measured and BMI will be calculated at screening only. Only weight will be measured at check-in and EOS.
- (h) A full physical examination will be performed at screening. A brief physical examination will be performed at check-in and EOS. Further details are provided in Section 6.2.5.
- (i) Further details on vital sign measurements are provided in Section 6.2.3.
- (j) Collected for healthy control subjects only.

- (k) Collected for hepatically impaired subjects only.
- (l) Further details on ECG recordings are provided in Section 6.2.4.
- (m) Further details on clinical laboratory assessments, including a complete list of assessments, are provided in Section 6.2.2.
- (n) Further details on drug/alcohol screening are provided in Section 6.2.2.
- (o) Women of childbearing potential only.
- (p) The time of aramchol dosing will be called “0” hour and occurs on the day denoted with grey shading. Further dosing details are provided in Section 5.1.
- (q) Further details on the collection of blood samples for PK analysis are provided in Section 6.1.
- (r) Further details on collection and reporting of AEs are provided in Section 6.2.1.

3.2 SCHEDULE OF EVENTS - MULTIPLE DOSE ARAMCHOL (PART 2)

Procedure ^(a)	Phase	Screening -28 to -2	Check-in -1	Treatment Period													EOS ^(b) 27 (±2)
	Day			1	2	3	4	5	6	7	8	9	10	11	12	13	
Admission to clinic			X														
Discharge from clinic															X		
Outpatient visit																X	
Informed consent		X															
Demographics		X															
Serology ^(c)		X															
Serum FSH ^(d)		X															
Inclusion/exclusion criteria		X	X														
Medical history		X	X														
Height, weight, and BMI ^(e)		X	X													X	
Physical examination ^(f)		X	X													X	
Vital sign measurements ^(g)		X	X	X	X	X	X	X	X	X	X	X	X	X	X	X	
12-lead ECG ^(h)		X	X				X				X			X		X	
Clinical laboratory testing ⁽ⁱ⁾		X	X				X				X			X		X	
Urine drug/alcohol screen ^(j)		X	X														
Urine pregnancy test ^(k)		X	X													X	
Aramchol administration ^(l)				X	X	X	X	X	X	X	X	X	X	X	X		
PK blood sample collection ^(m)				X			X				X	X	X	X			
AEs ⁽ⁿ⁾		← X →															
Prior/concomitant medications		← X →															

Abbreviations: AE, adverse event; BMI, body mass index; ECG, electrocardiogram; EOS, end of study; FSH, follicle-stimulating hormone; PK, pharmacokinetic. Notes:

- (a) When procedures overlap or occur at the same time point, all blood draws should follow vital sign measurements or ECGs, and PK sampling should be timed to occur last and as close to the scheduled time window as possible.
- (b) An EOS visit will occur 14 (±2) days after discharge from clinic.
- (c) A complete list of serology assessments is provided in Section 6.2.2.
- (d) Females only. Further details are provided in Section 6.2.2.
- (e) Height and weight will be measured and BMI will be calculated at screening only. Only weight will be measured at check-in and EOS.
- (f) A full physical examination will be performed at screening. A brief physical examination will be performed at check-in and EOS. Further details are provided in Section 6.2.5.
- (g) Further details on vital sign measurements are provided in Section 6.2.3.
- (h) Further details on ECG recordings are provided in Section 6.2.4.
- (i) Further details on clinical laboratory assessments, including a complete list of assessments, are provided in Section 6.2.2.
- (j) Further details on drug/alcohol screening are provided in Section 6.2.2.

- (k) Women of childbearing potential only.
- (l) Aramchol dosing occurs twice daily (approximately 12 hours apart) on days denoted with grey shading. Further dosing details are provided in Section 5.1.
- (m) Further details on the collection of blood samples for PK analysis are provided in Section 6.1.
- (n) Further details on collection and reporting of AEs are provided in Section 6.2.1.

